12.2. NORMALIZED CONSUMPTION INDEX AND REDUCED NORMALIZED CONSUMPTION INDEX

12.2.1. Definitions

According to the CIP (Appendix 3), the Consumption Index (CI) will be define as the sum of all resources consumed, weighted for the contribution of unit cost of each event to the total cost:

$$CI = \sum_{j=1}^n \alpha_j E_j$$

where E_j is the observed value of event j and α_j is the ratio between unit cost of event j and the total cost. The Normalized Consumption Index will be define as a transformation of CI such that it ranges between 0 and 1. The simplest definition is

$$NCI = \frac{CI}{1 + CI}$$

The contributions of each event on the total cost (α_j) are reported in Table 5 and are calculated using result of 4 European countries (Italy, France, Germany, UK).

Table 5 : Contributions of each event on the total cost

Event (within discharge)	a_j	a*_j
OR time (hours – only first attempt)	0.1114	0.1177
Re-operation up to discharge (yes/no) [valve intervention within discharge]	0.2251	
ICU LOS (days)	0.0798	0.0843
Ward LOS (days)	0.0254	0.0268
Transfusion (units during implant and ICU)	0.0093	
Sepsis (yes/no) [from AE]	0.2544	
Was the subject under renal replacement (RRT) therapy in ICU? (yes/no)	0.0092	

Any Permanent Pacemaker Implant	0.2006	
Stroke (yes/no) [from AE]	0.2182	

Since OR time and hospital cost represent more than 95% of total cost for all countries, a reduced Normalized Consumption Index (rNCI) will be define as the previous index but using only OR time, ICU and ward length of stay ($\alpha * j$).

Descriptive analyses for NCI, rNCI, and their components will be reported overall, by treatment and stratified by country.

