12.2.2. Testing strategy and analysis

As co-secondary analysis, Normalized consumption index and Reduced normalized consumption index will be analyzed in a superiority context. A one-sided superiority test will be conducted comparing the treatment and control group at discharge in order to reject the null hypothesis that PERCEVAL is not superior to Stented valve, according to the following hypotheses:

$$H_0: \mu_{\text{PERCEVAL}} \geq \mu_{\text{CONTROL}}$$

$$H_1: \mu_{\text{PERCEVAL}} < \mu_{\text{CONTROL}}$$

where μ_{PERCEVAL} and μ_{CONTROL} are the Normalized and Reduced normalized consumption indexes of PERCEVAL and Control groups, respectively. Since statistical significance is needed for both time endpoints for claiming superiority on consumption index, no adjustment of multiplicity is necessary.

If less than 5% of data for consumption indexes are missing, the analyses will be based on the complete cases and the comparison will be done by means of Wilcoxon-Mann-Whitney tests.

Otherwise, a multiple imputation process will be applied. In case of non-normality, data will be transformed toward normality before imputation using a logarithmic transformation. Treatment groups will be compared using Multiple Imputation (MI) approach and an ANCOVA model. Mean values of NCI and rNCI will be analyzed based on observed and imputed data. Multiple imputation will be performed under the assumption of missing-at-random (MAR) and will be implemented in using regression multiple imputation. The regression model will include as explanatory variables the treatment, surgical approach and the presence of concomitant procedures. No rounding or range restrictions will be applied. Imputed data will consist of 300 imputed datasets. The random seed number for the regression multiple imputation will be 9877. Each of the 300 imputed datasets will be analyzed by means of an ANCOVA analysis using the observed/imputed values as the dependent variable. The model will include as fixed effect categorical factors for treatment groups. Results from analysis of each imputed dataset, i.e., LSM treatment differences and their standard errors, will be combined using Rubin's imputation rules to produce a pooled LSM estimate of treatment difference, its 95% confidence interval, and a pooled p-value for the test of null hypothesis of no treatment effect.

In case of imputation, sensitivity analyses will be performed using complete cases and Wilcoxon-Mann-Whitney tests.

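### If 5% or more of consumption-index values are missing, SAP 12.2.2 appears to impute the whole index without the patient's recorded components: a modest loss of precision, and bias if missingness depends on those components differently by arm

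*SAP*

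**What the plan says.** SAP 12.2.1 defines a consumption index CI as a weighted sum of nine separately recorded items (Table 5), and NCI = CI/(1+CI). The rNCI uses only operating-room time, ICU stay and ward stay, with slightly different weights.

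SAP 12.2.2 tests both indexes for superiority, one-sided, and requires both to be significant before superiority on consumption is claimed. On missing data it says:

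- Below the trigger: "If less than 5% of data for consumption indexes are missing, the analyses will be based on the complete cases", compared by Wilcoxon-Mann-Whitney tests.
- Otherwise: "Multiple imputation will be performed under the assumption of missing-at-random (MAR) and will be implemented in using regression multiple imputation". Non-normal data are log-transformed first. On the predictors: "The regression model will include as explanatory variables the treatment, surgical approach and the presence of concomitant procedures".
- Analysis: "Mean values of NCI and rNCI will be analyzed based on observed and imputed data", and "Each of the 300 imputed datasets will be analyzed by means of an ANCOVA analysis using the observed/imputed values as the dependent variable". Treatment is the only factor named for that ANCOVA.
- If imputation was used, "sensitivity analyses will be performed using complete cases and Wilcoxon-Mann-Whitney tests".

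Nothing in the text available says how an index is formed when one item is missing. The only component-level fill is in SAP 18.12, where missing ICU admission and discharge clock times are set to fixed values.

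**The concern.** Most of a patient's index is usually known even when one item is blank. Imputing the total from arm, approach and concomitant procedure replaces that knowledge with a draw around a group mean. Two things follow. Precision is lost that the recorded items could recover. And the missing-at-random assumption has to hold given three variables only, so it fails if items are more often incomplete in, say, long ICU stays. If that pattern also differs by arm, which is possible in an unblinded trial, the superiority test is biased.

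The same SAP does otherwise in 11.2.1: missing haemodynamic values are imputed from the patient's own other assessments, with country, surgical approach, gender and age. The introduction to the protocol (section 3) names superiority in resource consumption at discharge as something the trial is meant to show.

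**Working it through.** The documents give no SD, effect, power or missing rate for NCI or rNCI, so there is no planned figure to reproduce. The checks use the Table 5 weights, 1:1 allocation (SAP 2.4) and one-sided 0.025 (protocol 10.2 sets 0.05 two-sided for secondary endpoints). Component distributions and missingness mechanisms are assumptions.

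**1. One patient.** Assume 4 h in the operating room, 10 ICU days, 10 ward days, no other events, and only the renal-replacement answer missing (weight 0.0092).

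- CI without it: 4(0.1114) + 10(0.0798) + 10(0.0254) = 1.498; NCI = 1.498/2.498 = 0.600.
- CI with it: 1.507; NCI = 0.601. The unknown part is worth about 0.0015.
- For an assumed typical stay (4 h, 2 ICU days, 8 ward days), CI = 0.808 and NCI = 0.447.

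If 0.447 is near the group mean, the plan draws this patient's value around a centre about 0.15 too low to settle an uncertainty of 0.0015.

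**2. Precision.** With no informative predictors, imputation does about as well as complete cases, so SE inflation at missing fraction m is about 1/√(1−m) − 1. A simulation (1,100 patients, 1,500 runs per scenario, 20 imputations, Rubin's rules) made ward stay the missing item, completely at random, with no true difference. The plan's model (log index on the three predictors) was compared with imputing log ward stay from those predictors plus the observed components, then rebuilding the index.

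| Missing | Formula | SE, full data | SE, plan | Inflation | SE, component-level | Inflation |
|---|---|---|---|---|---|---|
| 5% | 2.6% | 0.00401 | 0.00411 | 2.5% | 0.00402 | 0.25% |
| 10% | 5.4% | 0.00400 | 0.00423 | 5.8% | 0.00404 | 1.0% |
| 20% | 11.8% | 0.00400 | 0.00449 | 12.3% | 0.00407 | 1.75% |

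**3. Bias where it is not expected.** With no true difference, and missingness either completely random or tied to ICU stay equally in both arms, the plan's bias was at most 0.00013 and its one-sided type I error 0.017 to 0.030. With a true difference of about −0.0054 and the ICU-linked mechanism shared by both arms, the bias reached −0.00023 at 20% missing, about 4% of the effect.

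**4. Bias where missingness differs by arm.** Long ICU stay makes ward stay missing in the Perceval arm only, with no true difference:

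| Missing | Bias, plan | Bias, complete case | Type I, plan | Type I, complete case | Type I, component-level |
|---|---|---|---|---|---|
| 5% | −0.0037 | −0.0038 | 0.145 | 0.153 | 0.027 |
| 10% | −0.0065 | −0.0067 | 0.343 | 0.359 | 0.021 |
| 20% | −0.0111 | −0.0115 | 0.731 | 0.763 | 0.027 |

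Negative values favour Perceval. The simulation error on a rate of 0.025 is √(0.025 × 0.975/1500) = 0.004. Complete cases were analysed on means, not by the planned rank test.

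**5. The rule that both indexes must be significant.** With a minor item missing under the same kind of mechanism (1,110 patients, 3,000 runs, complete-case means standing in for the plan's model), NCI alone gave type I errors of 0.18 and 0.63 at 8% and 15% missing, but the joint claim stayed at 0.025 and 0.026. With ward stay missing at 8%, both indexes are lost for the affected patients. The joint false-claim rate was then about 0.5, and about 0.03 with component-level imputation.

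**The case against.** The strongest reply is that this may never matter, and much of it stands.

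**The trigger.** A reader might infer that 5% is easily reached: nine items each missing in 0.6% of patients give 1 − 0.994⁹ = 5.3%. The documents do not support that count. Table 5 takes sepsis and stroke from adverse-event records, and re-operation is a valve-intervention event. SAP 18.12 derives pacemaker implant from the SAE form and codes its composite event variables as no when no event is recorded. That leaves about five items that can be blank (operating-room time, ICU stay, ward stay, transfusion, renal replacement): 1 − 0.994⁵ = 3.0%, below the trigger. About 1% per item without overlap is needed (1 − 0.99⁵ = 4.9%). One caution remains: ward time is derived as hospital time minus ICU time, so a missing ICU date removes two items and both indexes.

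**The bias.** A reader might infer that the planned test is biased. Nothing in the documents suggests component-dependent missingness that differs by arm. The mechanism in step 4 is deliberately one-sided; it illustrates the risk and does not predict it.

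**The joint rule.** It protects the claim when only a minor item is missing. It does not when a main item is.

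**Adding rNCI as a predictor.** This looks like an easy remedy for NCI, but it is available only when rNCI is observed, which is where the joint rule already limits the harm.

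**The range.** SAP 12.2.1 says "The Normalized Consumption Index will be define as a transformation of CI such that it ranges between 0 and 1", while 12.2.2 says "No rounding or range restrictions will be applied". It is tempting to call this an error. But the simulated SE of 0.0040 implies an SD of 0.0040 × √(1100/4) = 0.066. For an assumed CI of 0.5 to 1.2, NCI is 0.33 to 0.55, so both bounds lie at least 5 SD away. No practical effect was shown.

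**Unseen text.** Protocol 6.3 refers to Appendix 3 for how the index is calculated, and its content is not reproduced. It may say how a missing item is handled. The SAP does not state outright that components are left unimputed.

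**Conclusion.** The point holds as an avoidable weakness in a contingency analysis of a secondary endpoint. On its natural reading, SAP 12.2.2 discards recorded components when it imputes. The firm part is efficiency: SE about 3% to 12% larger at 5% to 20% missing, against about 0.3% to 2% with component-level imputation.

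Bias is conditional. It was negligible with random missingness and, under the null, with a mechanism shared by both arms. It became serious only when missingness followed the components differently by arm. The claim on both indexes is then exposed mainly when operating-room, ICU or ward time is the missing item. Because complete cases carry nearly the same bias, agreement between the main and sensitivity analyses would not be reassuring.

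The sizes rest on assumed component distributions, ward stay as the missing item and about 1,100 patients. Component-level imputation removes the bias only where missingness depends on observed components.

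**What to change.** In SAP 12.2.2, impute the missing component or components, using all observed components plus treatment, surgical approach and concomitant procedure as predictors. Then recompute CI, NCI and rNCI in each of the 300 datasets before the ANCOVA and pooling. State explicitly how an index is handled when one item is missing, and align this with protocol Appendix 3.

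The cost is a slightly larger imputation model and a few lines of code. No new data are needed, and the 5% trigger and the joint significance rule can stay as they are.

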12.3. HEALTH STATUS (EQ-5D-5L)

The number and proportion of subjects of each level (1 - no problems, 2 - slight problems, 3 - moderate problems, 4 - severe problems, 5 - extreme problems) for each dimension (mobility, self-care, usual activities, pain/discomfort, and anxiety/depression) will be reported. The change in numbers and proportions from baseline to post-implant FU will be calculated⁹. The tables will be shown by treatment arm.

The Paretian classification⁹ will be applied at each available post-implant FU according to the following rules:

- A health profile is better than another if it is better in at least one dimension, and is no worse in any other dimension.
- A health profile is worse than another if it is worse in at least one dimension, and is no better in any other dimension.

Using this principle to compare a patient's EQ-5D health states between any two time periods, there are only 4 possibilities:

1. Their health state is better
2. Their health state is worse
3. Their health state is exactly the same
4. The changes in health are 'mixed': better on one dimension, but worse on another.

According to the above classification, changes from baseline in health status by treatment arm will be reported. Additionally, changes from baseline will be displayed as pie charts (by treatment and by each available post-implant assessment).

EQ-5D-5L answers to each dimension (health states) will be converted into a single index value. The index values allow the calculation of quality-adjusted life years (QALYs) that are used to inform economic evaluations of health care interventions. The idea underlying the QALY is that a year of life lived in perfect health is worth 1 QALY (1 Year of Life × 1 Utility = 1 QALY) and that a year of life lived in a state of less than this perfect health is worth less than 1. In order to determine the exact QALY value, it is requested to multiply the index value associated with a given state of health by the years lived in that state. The steps to obtain a QALY are:

1. Each dimension of the EQ-5D-5L questionnaire will be scored as follow:
 - Level 1 will be coded as '1'
 - Level 2 will be coded as '2'
 - Level 3 will be coded as '3'
 - Level 4 will be coded as '4'
 - Level 5 will be coded as '5'
 - Missing or ambiguous values (e.g. 2 boxes are ticked for a single dimension) will be coded as 'g'.

All five responses are then combined for a five-digit health state. For each five-digit health state there is a correspondent health related quality of life or score. The example in Figure 2 identifies the state '12345'.

- Each individual response to EQ-5D-5L will be converted into a single utility value by applying value sets reported in Appendix I (provided by the EuroQol website). UK coefficients will be used as primary analysis (they represent the standard). Since Germany and France will represent the top enrolling countries, the Germany-based and France-based scoring system will be used as sensitivity analyses in order to assess the robustness of results changing the country value sets. States including '9' will not be set as missing.

For example, the state '12345' would be converted in an utility value of 0.063 using the UK value set.

- The utility values will be calculated for each patient at each available time point. An averaged index value will be calculated for each time interval (i.e., Baseline – M3, M3 – Y1) as:

$$QALY_{Vi \rightarrow Vj} = k * (utility_{Vi} + utility_{Vj}) / 2$$

where $QALY_{Vi \rightarrow Vj}$ is the averaged quality of life between V_i and V_j , $utility_{Vi}$ and $utility_{Vj}$ are the utility values at visit V_i and V_j respectively, and k is a weight representing the portion of year that $V_i - V_j$ covers:

$$k = (\text{date of EQ5D at } V_j - \text{date of EQ5D at } V_i) / 365.25$$

In order to use the $utility_{Vi}$ and $utility_{Vj}$ data, the following criteria should be met:

- For M3: $(\text{date of EQ5D at M3} - \text{date of EQ5D at Baseline}) / 365.25$ is lower or equal to 0.3;
- For Y1: $(\text{date of EQ5D at Y1} - \text{date of EQ5D at Baseline}) / 365.25$ is between 0.9 and 1.1.

The quality of life between baseline to a specific time point V_i is given by the sum of all time-interval QALY from baseline to V_i . No discount rate will be applied, since evaluation is performed at 1 year.

Figure 2: Example of EQ-5D-5L form

Under each heading, please tick the ONE box that best describes your health TODAY

MOBILITY			
I have no problems in walking about			Level 1 is coded as a '1'
I have slight problems in walking about			
I have moderate problems in walking about			
I have severe problems in walking about			
I am unable to walk about			
SELF-CARE			
I have no problems washing or dressing myself			Level 2 is coded as a '2'
I have slight problems washing or dressing myself			
I have moderate problems washing or dressing myself			
I have severe problems washing or dressing myself			
I am unable to wash or dress myself			
USUAL ACTIVITIES (e.g. work, study, housework, family or leisure activities)			
I have no problems doing my usual activities			Level 3 is coded as a '3'
I have slight problems doing my usual activities			
I have moderate problems doing my usual activities			
I have severe problems doing my usual activities			
I am unable to do my usual activities			
PAIN / DISCOMFORT			
I have no pain or discomfort			Level 4 is coded as a '4'
I have slight pain or discomfort			
I have moderate pain or discomfort			
I have severe pain or discomfort			
I have extreme pain or discomfort			
ANXIETY / DEPRESSION			
I am not anxious or depressed			Level 5 is coded as a '5'
I am slightly anxious or depressed			
I am moderately anxious or depressed			
I am severely anxious or depressed			
I am extremely anxious or depressed			

Levels of perceived problems are coded as follows:

Descriptive statistics of the change from baseline of the QALY and EQ-5D index values (continuous) at each FU assessment will be shown as described in section 5.2.

Linear mixed model for repeated measures (MMRM) will be applied to compare EQ-5D index values between the two groups. EQ-5D index values will be adjusted by baseline index value, time point, and treatment-by-time interaction. Patient will be also added to the model as a random variable. Estimates of the least square means for EQ-5D index values and 95 % confidence intervals (CIs) will be calculated by each visit and group.

Descriptive statistics of the change from baseline of the EQ VAS data (continuous) at each FU assessment will be shown as described in section 5.2.

Mann-Whitney tests will be applied to compare treatments in terms of EQ-5D index values and EQ VAS data.

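### SAP 12.3 says EQ-5D-5L states with an unanswered item are not set as missing, gives no rule to score them, and conflicts with SAP 18.5

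*SAP*

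**What the plan says.** SAP 12.3 sets out the scoring in steps.

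- Each dimension is coded by its level, up to "Level 5 will be coded as '5".
- A separate code covers incomplete answers: "Missing or ambiguous values (e.g. 2 boxes are ticked for a single dimension) will be coded as" that code.
- The five codes are joined into a state, and "For each five-digit health state there is a correspondent health related quality of life or score".
- "Each individual response to EQ-5D-5L will be converted into a single utility value by applying value sets reported in Appendix I". The UK set is primary; the German and French sets are for sensitivity.
- The same step then adds: "States including '9' will not be set as missing".
- Utilities then go into the QALY: "The utility values will be calculated for each patient at each available time point".

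The index values also feed the MMRM, which adjusts for the baseline index, and the Mann-Whitney comparison at the end of 12.3. The five-item profiles feed the Paretian classification of change from baseline.

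Two other places bear on the point. SAP 18.5 gives a general rule that missing values count as missing in the analysis. Protocol 10.8 allows missing data to be replaced by a suitable method, provided the SAP describes it.

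**The concern.** A programmer following 12.3 literally must keep an incomplete state as non-missing and convert it to a utility, but the section defines only levels 1 to 5 and offers no default, proration or imputation for anything else. The instruction also points the opposite way from 18.5. Where this SAP does intend imputation, it says so in detail: 11.2.1 (hemodynamics) and 12.2.2 (consumption indexes) both give a model, a number of imputed datasets and a seed. Section 12.3 has nothing comparable for EQ-5D items.

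Incomplete forms are foreseen, since 12.3 itself gives two ticked boxes as an example, and the 1-month form is self-administered (protocol 4.2). Quality of life is a listed secondary endpoint (protocol 8.5.8). The trial is non-blinded (protocol 8.1) and sponsor personnel run the main analysis (SAP 4.1), so a scoring choice left unwritten would be open to question later. The same gap arises under all three value sets.

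**Working it through.** **The plan's own figure.** The only number tied to the scoring is the worked example: "For example, the state '12345' would be converted in an utility value of 0.063 using the UK value set". It cannot be reproduced, because the Appendix I value sets are not in the supplied text. It uses valid levels only, so it does not show how an incomplete state would be scored.

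**1. How many states have no stated rule.**
- Five items with five levels: 5^5 = 3,125 states.
- Adding one code for a missing answer: 6^5 = 7,776 states.
- States with at least one missing code: 7,776 − 3,125 = 4,651.

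Section 12.3 gives a route to a utility for the 3,125 and none for the 4,651. This counts possible states; it is not a forecast of how many patients are affected.

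**2. The two rules side by side.** SAP 12.3 keeps states with a 9 as non-missing. SAP 18.5 treats missing values as missing. A specific section may override a general one, but only if it then says what value to use, and 12.3 does not.

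**3. Weight of one visit's utility in the one-year QALY.** Each interval contributes k × (u_i + u_j)/2. Summing Baseline–M3 (length k1) and M3–Y1 (length k2), where M3 is the 1-to-3-month visit:

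QALY = k1(u0 + uM3)/2 + k2(uM3 + uY1)/2

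- The weight on uM3 is (k1 + k2)/2.
- Section 12.3 requires the Y1 form to fall 0.9 to 1.1 years after baseline, so k1 + k2 = 0.9 to 1.1 and the weight is 0.45 to 0.55.
- For an assumed scoring error of 0.10 in uM3, the patient's QALY moves by 0.10 × 0.45 = 0.045 to 0.10 × 0.55 = 0.055.
- The weight on u0 is k1/2, at most 0.3/2 = 0.15 under the 12.3 limit for M3.

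The 0.10 is illustrative; the documents give no figure for it.

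**4. Paretian step, if 9 were read as a number.** The SAP does not say that it would be, so this shows only what the silence permits.
- A follow-up profile unchanged except for one unanswered item is classed as worse in every case (3,125 states × 5 items = 15,625 comparisons, all worse).
- The same gap at baseline reverses the sign: 92345 to 12345 is classed as better.

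**The case against.** The strongest reply is that the sentence is harmless in practice. If the value sets hold no entry for a state with a 9, the look-up returns nothing, the index is blank, and 18.5 then applies. On that reading the sentence means only that the record is retained, or it is a slip for the opposite instruction. This has force: the documents do not show an intention to score blanks, and it would be wrong to say that the plan corrupts the endpoint. What remains is that the text says one thing and the benign reading needs another. Version 4.0 of the SAP amended 12.3, and the sentence still stands in version 5.0 without explanation.

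Three stronger readings are tempting but are not supported.

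- **Two different missing codes.** The supplied text prints the code as the letter g in the list and as 9 later. This is very probably a PDF-reading artefact. The other codes are digits, the SAP describes a five-digit state, and the later sentence plainly refers back to the same code. It is not an error in the plan.
- **No utility exists for such states.** That is a reasonable inference from the 1-to-5 scoring, but Appendix I is not available to check. The documents support only that the supplied text gives no utility or scoring rule.
- **A known size of bias.** Any rate of incomplete forms, or any assumption that blanks are scored at level 1 or level 5, would come from outside the documents.

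**Conclusion.** The point stands as a wrong or, at best, self-contradictory analysis rule. SAP 12.3 tells the analyst not to set incomplete EQ-5D states to missing, supplies no way to value them, and conflicts with 18.5. It may be a slip for the reverse instruction.

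Its reach is limited to secondary analyses: the EQ-5D index (MMRM and Mann-Whitney), the QALYs and possibly the Paretian classification. Nothing in the primary MACCE analysis, the alpha or the sample size depends on it. The effect on any treatment comparison cannot be sized, because it depends on item missingness and on the value an analyst would choose, and neither is given. The importance is minor. The case for acting is that the correction is clear and nearly free.

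**What to change.** Amend SAP 12.3 as follows.

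1. Replace the sentence with a rule that a profile with any missing or ambiguous item has its index value set to missing at that visit, in line with 18.5. If the sponsor prefers item imputation, the method must be written out in full.
2. Exclude such profiles from the Paretian comparison, at baseline and at follow-up.
3. Drop any QALY interval that needs the missing utility, and treat the one-year QALY as missing when an interval is lost. Summing only the remaining interval would cover less than the year. A missing M3 utility removes both intervals.
4. State how a missing baseline index is handled in the MMRM. It is an adjustment covariate there, so relying on the model to absorb missing outcomes does not cover it. Nor does the MMRM cover the Mann-Whitney tests or the QALYs, so say that these use the profiles with a valid index.

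The cost is a few sentences in the SAP before the analysis is run. No new data, protocol change or sample-size work is needed.
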